**C-SSRS Screener Monitoring.** Clinical team members will review responses to the C-SSRS and conduct outreach based upon recent and/or current suicidal ideation and/or suicidal or self-harm behaviors. Specifically, we will outreach if the participant positively endorses thinking about how they may kill themselves, have had thoughts of killing themselves with intention of acting on these thoughts, and/or if they've started to work out details of how to kill themselves.

Using the same clinical thresholds described above, the Cogito app will send an automatic notification to the participant regarding their scores, as well as resources (e.g., Military and Veterans Crisis Line, Military OneSource, Military Health System provider contact information [individualized data entered by participant or study team]).

**Cogito Model Score Monitoring.** Model scores are presented both in number and color format (Figure 4). Red indicates scores 39 or below, yellow indicates scores between 40 and 79, and green indicates scores between 80 and 100. The higher the score, the "healthier" the individual's behaviors. Any drastic daily change in score (+/- change of 20) and/or two scores less than 20 may prompt a clinical outreach call.

**Active Control.** Participants randomized to the Active Control group will download MyCAP and have access to resources housed within this app for a three-month period post-consent. Participants will be provided information regarding the mHealth Tool apps, and provided basic information on how to download the apps. As noted above, participants will be provided biweekly surveys as listed in Table 1. Participants will get one notification when surveys are available. If surveys are not completed, participants may be sent a reminder to complete the surveys via MyCAP automatic reminder or the in-app messaging feature.

**Clinical Research Staff Outreach – Active Control.** Clinically-trained research team members will monitor the MyCAP dashboard each business day one time per day (excluding federal holidays and weekends); however, outreach will solely be based on survey data or lack thereof.

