## **E. Potential Scientific Problems**

Participant recruitment and retention may be a potential scientific concern; however, we have initial support from Naval command to recruit onboard an aircraft carrier (~5000 Sailors) and attached Striker units. The PI and [name] will continue to work with Naval command to ensure ongoing recruitment support and planning.

Technological issues with Android and/or iPhone platforms with the assigned study arms (Active or Control) may occur. The study team has pilot data that assists in problem-solving these concerns quickly. Cogito Corporation will have dedicated staff to assist with any Cogito Companion technological issues as they arise. The study team will monitor MyCAP issues and work closely with REDCap staff at the University in a timely manner. Issues will be documented and reviewed as part of Aim 2 and appropriate amendments may occur with consistently identified issues.

While 21% attrition is expected and the statistical methods proposed below are equipped to handle data that are missing at random, characteristics of participants who drop out of the study will be compared to those who do not and if there is differential dropout by group or it is plausible, based on characteristics of those who did drop out, that the missingness is related to the primary outcome of interest, additional methods aimed at accounting for nonignorable dropout will be employed where possible.

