## F. Data Analysis Plan

**Power Analysis.** Power is calculated for the two primary hypotheses assessing episodes of distress and distress over the course of the study. We will recruit 1418 participants and expect approximately 33% to decline participation resulting in 950 participants randomized to either the Cogito Companion or Active Control groups, stratified by gender, force and phone type. Assuming 21% attrition, it is expected that 750 participants will complete the entire protocol. While the analysis will include all participants who are randomized, power is based on 750 completed (375 per group). Power to address episodes of distress was estimated using the Poisson regression procedure in Power and Sample Size (PASS) v13. An episode of distress is defined as an OQ-45 total score of  $\geq 64$  with each participant having a maximum of 6 possible episodes (every 2 weeks for weeks 2-12 of the study, inclusive). We wish to detect a 15% difference in the number of episodes of distress over the 3-month study period, and we assume a two-sided test and a significance level of 0.025 to control for the two primary tests (number of episodes and overall distress). If the Active Control mean response rate is 3.5 (i.e., number of episodes in the 3-month study period) we will have 97% power to detect a 15% difference. For Active Control response rates of 3, 2.5, 2 and 1.5, power is then 94%, 89%, 81% and 68%, respectively. For the second primary hypothesis, we will calculate the Area Under the Curve (AUC) using an estimate statement within a linear mixed model described below. We wish to demonstrate that the Cogito Companion is superior to Active Control by a margin of at least 14 points (minimally clinically significant difference, translates to an AUC difference of 84). Using the Superiority by a Margin procedure in PASS v13, 375 participants per group provides 90% power to demonstrate superiority, assuming a true difference of  $\geq 18.7$  points (AUC difference of 112.2) with a significance level of 0.025.

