**Analysis Plan.** All analyses will assume a two-sided test of hypothesis, a significance level of 0.05 (unless otherwise indicated) and will be run in SAS v9.4 or higher, or R v3.3 or higher. To check randomization, demographic and clinical characteristics will be compared between groups using t-tests, chi-square tests or nonparametric tests, as appropriate. If any variable is found to be significantly different between the groups and is also plausibly associated with an outcome, it will be considered as potential confounders in the models described below.

**Aim 1.** To address the hypothesis regarding episodes of distress first using Poisson regression will be used to model the number (response rate) of episodes of distress as a function of group (0=Active Control, 1=Cogito), any potential confounders, and an offset of log (time) to account for varying lengths of follow-up. If the deviance is estimated to be  $> 1.5$ , Negative Binomial regression will be used instead, incorporating the same variables. The parameter estimate associated with the group variable will be exponentiated, providing an estimate of the ratio of response rates between the groups and will be reported with a 97.5% confidence interval (CI). To address the hypothesis regarding distress over the course of the study, a linear mixed-effects model will be employed with longitudinal OQ-45 scores as the dependent variable and group, potential confounders, and an interaction between group and time (using either natural cubic B-spline transformations on time or polynomial transformations on time) as independent variables. These transformations will also be applied to the random time effects so that individual trajectories can be calculated. Akaike's Information Criterion will be used to determine which model provides the best fit (both between the B-spline/polynomial models and within them). Once a final model is determined, the difference in AUC will be calculated and between groups and compared to the clinically meaningful AUC difference of 84 using a one-sided test. Here the null hypothesis is that  $AUC_{AC} - AUC_{Cogito} \geq 84$ , and the alternative hypothesis is that  $AUC_{AC} - AUC_{Cogito} < 84$ . The estimated difference will be reported with the one-sided 97.5% CI. For hypothesis 1.2, a Kaplan-Meier estimate will be used to compare the median time to treatment engagement

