between the groups and each median will be reported with 95% CIs. Treatment engagement is operationalized as a visit with any medical or mental health provider in which a mental health related ICD code is identified. and will be determined by medical record review. Additionally, the total number of mental health visits calculated from the CSRI-EU-R will be modeled using a Poisson or Negative Binomial regression model to estimate the difference in number of visits between the groups over the course of the study. The model will be set up similarly to the OQ-45 model. Hypothesis 1.3 is similar to hypothesis 1.1 such that we wish to look at episodes of depressive symptoms (PHQ-9), post-traumatic symptoms (PCL-5) and suicide-related thoughts (BSS) as well as severity of each over the course of the study. We also wish to look at perceived physical and psychological health functioning (RAND SF-36) over the course of the study. The methods employed to address hypothesis 1.1 will be utilized to estimate the difference in number of episodes of each outcome (excluding the SF-36) as well as the difference in AUC for each outcome. Zero-inflated negative binomial regression will be considered for the BSS if a large proportion of the participants do not exhibit suicidal thoughts and transformations will be considered for the AUC BSS analysis, given that it is likely to be highly skewed. Cutoffs for episodes of depressive/post traumatic symptoms, and suicidal thoughts are  $\geq 10$  (PHQ-9),  $\geq 33$  (PCL-5), and  $\geq 2$  (BSS), respectively.

***Aim 2.*** We will assess the proportion of participants who find the Cogito Companion acceptable, defined as  $\geq 70\%$  of participants scoring  $\geq 24$  on the CSQ. The proportion of Cogito Companion participants with a CSQ score of  $\geq 24$  will be calculated with a 95% CI. Additionally, the proportion of participants engaging in activities will be reported with a 95% CI as well as the median (range) amount of time spent on the application. Feasibility will be measured by the proportion of Cogito Companion participants who complete treatment and reasons for termination will be examined.

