NCT 04159480 Study Analysis Plan
Facilitating Assessment of At-Risk Sailors Using Technology (FAAST)
VA Eastern Colorado Health Care System
29 May 2023

Originally, members of the team obtained funding to conduct a randomized controlled trial (RCT) to test the efficacy of Cogito versus active control among Navy personnel; however, significant implementation challenges arose secondary to the COVID-19 pandemic. Thus, with permission from the study sponsor, aims were in part revised as follows: 1) evaluate the feasibility (application download/use and technical challenges) and acceptability (satisfaction) of the Cogito among a cohort of naval personnel; 2) longitudinally characterize time to risk identification by cohort (Cogito/Active Control); 3) identify patterns of symptoms (distress, depressive, post traumatic, suicide-related thoughts and mental and physical health functioning) over time and by study group. However, while the aims of the study changed, the team continued to follow Power Analysis and the original analysis plan. Please see the two sections provided below for greater insight into the changes. Grant funds were used to purchase the use of the Cogito Application for this study. The application is not available for general use, and other than providing technical support, the Cogito Team was not involved with data collection or analyses.

Original statistical analysis plan (SAP) from the protocol:

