Aim 2. We will assess the proportion of participants who find the Cogito Companion acceptable, defined as $\geq 70\%$ of participants scoring ≥ 24 on the CSQ. The proportion of Cogito Companion participants with a CSQ score of ≥ 24 will be calculated with a 95% CI. Additionally, the proportion of participants engaging in activities will be reported with a 95% CI as well as the median (range) amount of time spent on the application. Feasibility will be measured by the proportion of Cogito Companion participants who complete treatment and reasons for termination will be examined.

Exploratory Aim. To explore patterns of distress experienced by participants over the course of the study, individual OQ-45 curves modeled in Aim 1 will be qualitatively clustered into groups based on visual inspection of the trajectory patterns. Once distinct patterns are identified and labeled, baseline demographic and clinical characteristics of participants in each pattern will be summarized and reported. This will be performed for the entire sample, as well as within each group. This is considered a hypothesis generating aim. This analysis will be repeated for the PHQ-9, PCL-5, BSS and SF-36.”

Revised and approved aims of the new statistical analysis plan:

Aim 1 (Revised - 2022). Longitudinally characterize risk by cohort (Active Control – study measures pushed only; Cogito Companion – study measures pushed plus Cogito Companion application [includes feedback from passive monitoring models]). Hypothesis 1.1 First characterization of risk, post-model score availability (7 days after download of app for model scores, 14 days for stability), will occur more quickly for the Cogito Companion group.

Aim 2. Evaluate the acceptability and feasibility of the Cogito Companion among military personnel. Aim 2.1. Acceptability of Cogito Companion will be evaluated based on participant satisfaction, participant engagement in application-related activities, and time spent on the application. Aim 2.2. Feasibility of Cogito Companion will be evaluated based on participant retention and accrual, and number and type of technical challenges noted during implementation.

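### The exposure time in the distress-episode model is undefined; read as elapsed follow-up, it turns any gap in OQ-45 completion between arms into bias in the rate ratio

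*Protocol*

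**What the plan says.** Protocol section F (Analysis Plan, Aim 1) models the number of distress episodes on group and any confounders, with "an offset of log (time) to account for varying lengths of follow-up". It changes from Poisson to negative binomial regression if the deviance exceeds 1.5. The SAP repeats this text in its copy of the original plan. Neither document says whether time means days enrolled, days to last contact, or surveys answered.

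The Power Analysis defines an episode as an OQ-45 total of 64 or more at a biweekly assessment in weeks 2 to 12, with "each participant having a maximum of 6 possible episodes". It also says that "the analysis will include all participants who are randomized". For hypothesis 1.3, "The methods employed to address hypothesis 1.1 will be utilized to estimate the difference in number of episodes of each outcome", so the same offset applies to the PHQ-9, PCL-5 and BSS episode counts.

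On missing data, section E says that if dropout differs by group, or missingness plausibly relates to the primary outcome, "additional methods aimed at accounting for nonignorable dropout will be employed where possible". Missed surveys are foreseen in section A (Technical Challenges) and section D (Administrative Monitoring and Outreach).

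The SAP introduction says the aims were partly revised but "the team continued to follow Power Analysis and the original analysis plan". The revised first aim reads "Aim 1 (Revised - 2022). Longitudinally characterize risk by cohort" and concerns how soon risk is first characterized.

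**The concern.** The outcome is not an event watched continuously over days. It is a count over at most six scheduled questionnaires, and an unanswered one cannot yield an episode. The phrase about lengths of follow-up points towards elapsed time. On that reading, a participant who stays enrolled and skips two surveys gets full exposure and two fewer chances to score. Each skip is in effect counted as a non-episode.

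This does not need informative missingness. Even if skipping is completely random within each arm, a difference in completion between arms moves the ratio. Lower Cogito completion would look like fewer episodes, and lower control completion would hide a benefit. The longitudinal OQ-45 mixed model uses observed scores and does not share the problem.

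**Working it through.** **Inputs from the documents** (protocol section F): up to 6 assessments; two-sided 0.025; design ratio 0.85; control means of 1.5 to 3.5 episodes; 375 completers per arm; 950 randomized. **Assumed**, because the documents give no figures: completion rates and within-person correlation.

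**1. The plan's power figures reproduce.** Poisson-regression power for a 1:1 binary covariate is Φ{[√(Nλ)·|ln 0.85| − z·√4] / √(2 + 2/0.85)}, with N = 750 and z = 2.241. At λ = 3.5: √2625 × 0.1625 = 8.327; (8.327 − 4.483)/2.086 = 1.842; power 96.7%. The five rates give 96.7%, 93.9%, 89.0%, 80.7% and 67.9%, against the stated 97%, 94%, 89%, 81% and 68%. Those figures are not in question.

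**2. Expected ratio under each offset.** Let p be the probability that a control occasion is distressed, R the true ratio, and cD and cN the completion on distressed and non-distressed occasions.
- Elapsed time: R × cD(Cogito)/cD(control).
- Completed surveys: the same value × m(control)/m(Cogito), where m = p(arm) × cD + (1 − p(arm)) × cN.

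**3. Skipping unrelated to distress (cD = cN).** The completed-survey offset returns R. The time offset gives:
- R = 1, Cogito 80%, control 90%: 0.80/0.90 = 0.89.
- R = 1, Cogito 85%, control 90%: 0.85/0.90 = 0.94.
- R = 0.85, Cogito 90%, control 80%: 0.85 × 0.90/0.80 = 0.956.
- R = 1, Cogito 68%, control 80%: 0.68/0.80 = 0.85, the whole design effect.
- Equal completion: no bias.

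**4. Error rates by simulation.** Beta-binomial counts over 6 surveys, 375 per arm, correlation 0.5, and the plan's switch to negative binomial (reading its rule as deviance/df > 1.5). False rejection with no true effect, time offset; ranges span runs of 300 to 1,000 replicates:

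| Cogito vs control completion | Control mean 3.5 | Control mean 2 |
|---|---|---|
| 80% vs 90% | about 44% to 49% | about 9% to 11% |
| 85% vs 90% | about 11% | about 2% to 3% |

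At 80% vs 90%, the completed-survey offset gives 1% to 3%. The time-offset results vary with the correlation. A separate run of that case at correlations 0.3, 0.5 and 0.7 gave about 71%, 51% and 31% (mean 3.5) and 21%, 12% and 4% (mean 2). With robust variance, which the plan does not specify, the tabled cases give about 56% and 21%, then 14% and 7%.

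Reverse case (R = 0.85, control mean 3, Cogito 90%, control 80%): power under the plan's rule is about 3% with the time offset and 53% with completed surveys.

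With all randomized participants (950/2 = 475 per arm, mean 2, correlation about 0.33, 400 replicates), 70% Cogito vs 80% control gave a ratio of 0.87 and 36% false rejection. The completed-survey offset gave 0.8%.

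**5. Skipping related to distress.**
- Same pattern in both arms, R = 0.85, p = 3/6 = 0.5, cN = 90%. The time offset gives 0.850. The completed-survey offset at cD = 60% gives 0.85 × 0.75/0.7725 = 0.825; at 70%, 0.85 × 0.80/0.815 = 0.834; at 80%, 0.85 × 0.85/0.8575 = 0.843. With R = 1 both give 1.00.
- From that starting point, shift both Cogito completion rates by the same number of points. The completed-survey offset becomes the less biased one once the gap exceeds 0.7 to 2.3 points. With Cogito 5 points lower it gives 0.81 to 0.84, against 0.78 to 0.80 for the time offset.
- Different pattern by arm, R = 1, p = 0.5: control 80% on distressed and 90% on other occasions, Cogito 90% and 80%. Overall completion is 85% in each arm, yet both offsets give 0.90/0.80 = 1.125.

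**The case against.** The strongest reply is that the problem needs two conditions: time must mean elapsed follow-up, and completion must differ between arms. The text shows an undefined term, not a wrong analysis. If the team used the number of surveys answered, one sentence settles it. That stands.

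A reader might go further and infer that Cogito completion will be lower, so that the ratio is tilted towards Cogito. The protocol describes a reminder for uncompleted surveys only in the control arm, and the Cogito reminders it describes are for audio diaries. The documents do not support that inference. The control reminder is permissive ("participants may be sent a reminder to complete the surveys via MyCAP automatic reminder or the in-app messaging feature"). Section II says the Cogito app prompts users to complete the measures, section C (Study Procedures) pushes surveys through both apps, and sections C and D provide outreach for missing data in both arms. Only controls receive an extra biweekly survey, which could work the other way. A gap is possible; its presence, direction and size are not shown.

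Section E might be thought to cover the matter, since it says the methods handle data missing at random. It is worded for dropout and does not touch the offset, and under the time offset even random skipping biases the ratio when completion differs.

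It is also fair that the completed-survey offset is not better in every case. When distressed occasions are skipped more often, equally in both arms, it exaggerates a true effect modestly and the time offset does not. That stands as a named cost, although in the settings computed a completion gap of about two points or less reverses the ranking.

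Finally, the revised first aim does not test this ratio. That lowers the priority. It does not remove the point, because the SAP says the original plan was still followed.

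**Conclusion.** The point holds in conditional form. The exposure term is undefined. On its more natural reading, with skipping unrelated to distress, the rate ratio is multiplied by the ratio of completion rates: 0.89 for 80% vs 90%, 0.94 for 85% vs 90%. At the assumed correlation of 0.5, the consequence under the plan's rule runs from serious (about 44% to 49% false rejection) to negligible (about 2% to 3%), depending on the completion gap and the control mean. All completion rates and the correlation are assumptions. The documents do not establish that the episode result is biased, or in which direction. Equal completion removes the bias only if skipping is also unrelated to distress. This is a cheap improvement of lower priority.

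**What to change.** In Aim 1 of protocol section F and its copy in the SAP, make log(number of completed OQ-45s at weeks 2 to 12) the primary offset, with the plan's overdispersion rule or robust variance. Do the same for the PHQ-9, PCL-5 and BSS episode counts. Keep elapsed time, ending at dropout, as a sensitivity analysis. Report completion by arm, and extend the missing-data text in section E to intermittent skips, including skips related to distress. If the model has already been run, state which definition of time was used and report both offsets.

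Modelling positive surveys out of completed surveys with a log-link binomial is not a safe substitute unless it carries robust or beta-binomial variance. Plain binomial gave about 20% to 23% false rejection with equal completion and no effect.

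The cost is a sentence or two, using data already collected. Three downsides should be stated:
- Participants with no completed survey do not contribute, since log(0) is undefined. This is an exception to analysing everyone randomized.
- Distress-related skipping that is equal in both arms makes a true 0.85 read as 0.825 to 0.843.
- Distress-related skipping that differs by arm is not corrected by either offset.

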## **I. Hypotheses and Specific Aims**

**Aim 1.** Evaluate the efficacy of the Cogito Companion as an upstream suicide prevention intervention.

**Hypothesis 1.1.** Participants allocated to the Cogito Companion will report significantly fewer episodes of distress and less distress over the course of the study (Outcome Questionnaire-45; OQ-45) compared to those allocated to the Active Control group.

**Hypothesis 1.2.** Among those with episodes of clinically meaningful distress, those allocated to the Cogito Companion will more rapidly engage in treatment (medical record review and Client Services Receipt Inventory-EU-Revised; CSRI-EU-R) to address such symptoms versus those allocated to the Active Control group.

**Hypothesis 1.3.** Participants allocated to the Cogito Companion will report significantly fewer episodes of and less severe depressive (Patient Health Questionnaire-9; PHQ-9) and post-traumatic symptoms (Post Traumatic Stress Disorder Checklist-5; PCL-5), and suicide-related thoughts (Beck Scale for Suicide Ideation; BSS, Columbia-Suicide Severity Rating Scale Screener; C-SSRS Screener), as well as overall increased perceived physical/psychological health functioning (Rand 36-Item Health Survey; SF-36) over the course of the study compared to those allocated to the Active Control condition.

**Aim 2.** Evaluate the acceptability and feasibility of the Cogito Companion among military personnel (Sailors).

**Aim 2.1.** Acceptability of Cogito Companion will evaluate based on participant satisfaction (CSQ), participant engagement in application-related activities (e.g., leaving voice recordings), and time spent on the application. Acceptability refers to the suitability of an intervention from the perspectives of the participants.

**Aim 2.2.** Feasibility of Cogito Companion will be evaluated based on participant retention and accrual, and number and type (minor, moderate, severe) of technical challenges noted during implementation. Feasibility refers to the ease of implementation.

**Exploratory Aim.** Identify patterns of distress, depressive symptoms, post-traumatic symptoms, suicide-related thoughts, and perceived physical and psychological health functioning over the course of the study among the entire sample, as well as within the Cogito Companion and Active Control groups.

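### Time to treatment engagement (Hypothesis 1.2) is compared only through two Kaplan-Meier medians, with no between-arm test, effect measure or time origin, and the medians may not be reached (minor; applies if this hypothesis is reported)

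*Protocol*

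**What the plan says.** Hypothesis 1.2 (Protocol, section I) reads: "Among those with episodes of clinically meaningful distress, those allocated to the Cogito Companion will more rapidly engage in treatment". The Data Analysis Plan (section IV.F, Aim 1) gives the timing analysis in one sentence: "a Kaplan-Meier estimate will be used to compare the median time to treatment engagement". The rest of that sentence asks for one median per arm, each with its own 95% CI. The event is "a visit with any medical or mental health provider in which a mental health related ICD code is identified", and its source is the medical record. A second analysis follows: "the total number of mental health visits calculated from the CSRI-EU-R will be modeled using a Poisson or Negative Binomial regression model". The SAP reproduces all of this in the plan it quotes from the protocol and adds nothing to it.

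The section's general default is a two-sided test at 0.05. That sets a level but names no test for this endpoint. Nothing says whether the clock starts at consent, randomisation, app download or the first distress episode. The SAP's revised Aim 1 does give a starting point, but for a different endpoint, first characterization of risk.

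On status, the power analysis covers only the two primary hypotheses, both under Hypothesis 1.1. The SAP's revised aims omit Hypothesis 1.2, while its introduction says the original analysis plan was still followed.

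**The concern.** The hypothesis is about speed, so the analysis should yield an estimate of how much faster one arm engages. Two medians with separate intervals do not provide that. If a median is not reached, the planned comparison gives no number for that arm. The Kaplan-Meier curves would still exist, but the plan names no contrast to take from them. The visit-count model does compare the arms, but on number of visits rather than time to the first.

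Without a time origin the analysis cannot be reproduced, because different starting points give different risk sets and follow-up. The hypothesis is also restricted to people who have a distress episode during follow-up. The app is meant to reduce such episodes, so the two subgroups may differ in ways that randomisation does not balance. A difference between them could be misread as a randomised effect.

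**Working it through.** **Plan's own figure.** There is none to reproduce. The documents give no engagement rate, event count, hazard ratio or power for Hypothesis 1.2. Every rate below is an assumption.

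**Observation time.** The Military Health System data section gives four months of records: 4 × 365.25/12/7 = 17.4 weeks. The Power Analysis defines an episode as an OQ-45 total of at least 64 at weeks 2 to 12. From a first episode, follow-up is therefore 17.4 − 2 = 15.4 weeks at most and 17.4 − 12 = 5.4 weeks at least.

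**When a median exists.** With a constant hazard and cumulative engagement p by time T, median = T × ln 2 / (−ln(1 − p)). With T = 4 months:

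| p | 20% | 30% | 40% | 50% | 60% | 70% |
|---|---|---|---|---|---|---|
| median (months) | 12.4 | 7.8 | 5.4 | 4.0 | 3.0 | 2.3 |

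Below 50% the median lies outside the records. With the clock at the first episode, a median within 15.4 weeks needs four-month engagement of at least 1 − exp(−ln 2 × 17.4/15.4) = 0.543.

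**Simulation.** 2,000 trials per cell, with a constant hazard within strata. Assumed first-episode weeks 2/4/6/8/10/12 have probabilities .60/.14/.09/.07/.05/.05, with censoring at week 17.4. Eight strata (gender 80/20, force 60/40, phone 50/50) have assumed hazard multipliers 1.5, 1.25 and 1.0. The test is a stratified log-rank, two-sided 0.05. Columns are control v app engagement by four months.

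| | 20 v 30% | 30 v 40% | 40 v 50% | 50 v 60% | 60 v 70% |
|---|---|---|---|---|---|
| 250 per arm, from first episode: both medians reached | 0% | 0% | 0% | 12% | 95% |
| same: neither reached | 100% | 100% | 89% | 4% | 0% |
| same: log-rank power | 63% | 57% | 53% | 56% | 63% |
| same: log-rank significant, no difference in medians computable | 63% | 57% | 53% | 55% | 5% |
| 100 per arm, from first episode: both medians reached | 0% | 0% | 0% | 18% | 84% |
| same: log-rank power | 30% | 26% | 24% | 26% | 29% |
| 375 per arm, from randomisation: both medians reached | 0% | 0% | 0% | 50% | 100% |
| same: log-rank power | 88% | 83% | 80% | 81% | 87% |

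At 250 per arm the difference in cumulative engagement 13 weeks after a first episode could be estimated in every scenario: true difference 8 to 10 points, 95% CI half-width 7 to 9. At 100 per arm the half-width is 11 to 15. With equal rates of 30% or 50% the log-rank rejected in 4.9 to 5.3% of trials. A rerun without strata gave the same picture.

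**Separate intervals are not a test.** In a simpler simulation (four months for everyone, 112 or 187 per arm), equal hazards gave non-overlapping median CIs in 0 to 0.8% of trials. With a hazard ratio of 1.5 and control engagement of 60 to 70%, the CIs separated in 28 to 45%, against log-rank power of 71 to 93%.

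**Selection into the subgroup.** Model: six correlated OQ-45 scores (correlation 0.7, SD 20), control means of 1.5 to 3.5 episodes, exactly 15% fewer episodes with the app, and no app effect on care-seeking at a given severity. Then 51 to 84% of control and 45 to 77% of app participants have an episode, about 170 to 315 of 375 per arm, so 250 is mid-range. The subgroup rate ratio is 1.03 to 1.06 if care-seeking follows underlying severity and 0.89 to 0.98 if it follows current severity.

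**The case against.** The strongest reply is that this matters little. The hypothesis is not primary, the revised aims drop it, and only a general sentence in the SAP's introduction keeps it alive. Per-arm medians with CIs are acceptable description for such an endpoint. This stands, and it sets the weight.

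The simulations rest on assumed rates, episode timing and strata. That also stands. A reader might infer that the medians will fail; the documents do not support that, because they give no engagement rate. Moreover, at 50 v 60%, nearly all the trials with a significant log-rank but no computable difference had the app median reached and the control median not, so the planned output would still show a direction. It would not show a size.

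Two stronger readings are tempting but do not hold. First, a reader might see a conflict between the distress subgroup and the statement that "the analysis will include all participants who are randomized". That phrase contrasts randomised participants with completers in a paragraph on the two primary hypotheses. The analysis text opens with a reference to Hypothesis 1.2, which carries its population with it. Second, a reader might see a contradiction over the event source, since the hypothesis names both records and the CSRI-EU-R. The analysis plan gives each a role: records for timing, the CSRI-EU-R for visit counts.

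**Conclusion.** The point holds at minor weight, and only if Hypothesis 1.2 is reported. The plan names no between-arm test, effect measure or time origin for time to engagement. Whether the medians would be reached is unknown. Under a roughly constant hazard and the record window, four-month engagement below about 50% would usually leave one or both medians unreached although the same data support a between-arm estimate. Above about 60% that problem largely disappears; the missing contrast and time origin remain.

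The episode-subgroup comparison is not protected by randomisation. At the planned 15% reduction in episodes the modelled bias is small, and its direction depends on how care-seeking relates to severity. A reader might infer that this invalidates the comparison; the figures do not support that, but the comparison should be labelled for what it is.

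**What to change.** 1. Make the between-arm comparison a log-rank test with a Cox hazard ratio and 95% CI, stratified by gender, force and, if both platforms were enrolled, phone type; collapse sparse strata. Add the Kaplan-Meier difference in cumulative engagement, or in restricted mean time, with 95% CI at one horizon fixed in advance. Report medians only if reached. Lead with the estimate and CI, because subgroup power is modest.
2. State the time origin, for example the first OQ-45 score of at least 64, and label the episode-subgroup comparison as non-randomised. Add a supporting analysis from randomisation that randomisation does protect: all randomised participants, or those with a baseline OQ-45 of at least 64. Study Procedures places baseline measures before randomisation, but the Consent text lists them both before and after, so confirm that the score used came before.
3. Label anything added after the 29 May 2023 SAP as post hoc.

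A sensitivity analysis that adds CSRI-EU-R contacts is optional.

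The cost is SAP wording and modest programming on data already planned, plus post hoc status. The horizon is a trade-off: about 5 weeks after a first episode is observed for nearly everyone but gives 29 to 36% power for the cumulative difference, while 13 weeks gives 48 to 59% but relies on censoring for first episodes after week 4 (17.4 − 13 = 4.4), 26% under the assumed timing. The all-randomised analysis answers a different question: a lower engagement rate there may only reflect less distress (modelled ratio 0.85 to 0.95 at 15% fewer episodes, if care-seeking follows current severity).
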